3.2.1.1 Primary efficacy analyses

The primary endpoint of treatment success will be tested sequentially (hierarchical structure) with the first test being non-inferiority test based upon the treatment difference. A rejection of the null hypothesis will trigger superiority testing.

The two hypothesis tests are hierarchically structured so that the second test (superiority) will only be considered if the first test (non-inferiority) is accepted. The superiority test is powered

to detect an absolute difference of 18 %. There is no alpha adjustment for the second test as a result of the hierarchical testing.

The primary efficacy analysis will be based on the mITT population and repeated on the PP population in order to assess the robustness of the results.

The primary efficacy variable is the proportion of subjects with successful overall preparation evaluated with the scale (from 1 to 4) of the Cleansing Score as assessed by the colonoscopist.

A successful preparation will be defined as excellent (4) or good (3) preparation.

A failure preparation will be defined as:

- Fair (2) or poor (1) according to colon cleansing score,
- Any subject who did not have a colonoscopy based on the investigator's assessment of the cleansing (insufficient faecal output, unclear faecal discharge, etc.) or due to preparation related AEs,
- Any subject for whom cleaning was not adequate for evaluation,
- Any subject for whom rescue treatment (saline enema) was needed.

The proportion of subjects with successful colon cleansing (graded as excellent or good) will be summarised along with the 95 % CI using the standard Wald asymptotic CI using the following SAS code:

```
proc freq data=ADCC(where=(PARAM='Successful overall preparation' and MITTFL='Y'));
```

```
table AVALC / missing binomial(level='Yes' cl=wald);
```

by TRTP;

run;

The primary efficacy endpoint will be analysed using a logistic regression model including treatment and country as covariates as well as the interaction between treatment and country if it is significant (i.e. p < 0.10, as interaction tests have low power) using the following SAS code providing the adjusted proportions with their 95 % CI thank to ilink option, and with the option firth in the model with interaction since there might otherwise be a quasi-complete separation of data points affecting the validity of the model:

proc logistic data=ADCC(where=(PARAM='Successful overall preparation' and MITTFL='Y'));

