class TRTP(ref='KLEAN-PREP') COUNTRYC(ref='Largest country') / param=glm;

model AVALC(EVENT='Yes') = TRTP COUNTRYC TRTP*COUNTRYC /
link=logit firth;

lsmeans TRTP / cl ilink;

ods output lsmeans=lsm ModelANOVA=TestInter;

run;

N.B.: TRTP*COUNTRYC, firth and ModelANOVA=TestInter will be removed if the interaction is not significant.

The formal hypothesis test result (p-value) for treatment difference will be presented together with a two-sided 95 % CI for the treatment difference in success rates. The non-inferiority will be demonstrated if the lower limit of the 95 % CI of that difference is higher than -15 %. The treatment difference and its p-value assessed for -15 % margin will be estimated using the

26/62

following SAS code, since the logistic procedure does not provide adjusted treatment differences:

proc freq data=ADCC(where=(PARAM='Successful overall preparation' and MITTFL='Y'));

table TRTP / nopercent norow nocum;

ods output OneWayFreqs=TRTfreq;

run;

data estimates;

merge TRTfreq lsm; by TRTP; AVALC="N"; Count=Frequency*(1-Mu); output; AVALC="Y"; Count=Frequency*Mu; output; keep TRTP Frequency Mu AVALC Count;

run;

proc freq data=estimates order=data;

table TRTP*AVALC / alpha=0.05 riskdiff(noninf margin=0.15 column=2); weight Count; ods output PdiffNoninf=NonInf;

run;

If the non-inferiority is demonstrated, the superiority will be analysed based upon treatment difference. If the lower limit of the CI is greater than zero, Eziclen®/Izinova® will be proven to be superior to Klean-Prep®. The following SAS code will be used to get the superiority p-value:

```
proc freq data=estimates order=data;
table TRTP*AVALC / alpha=0.05 riskdiff(sup column=2);
weight Count;
ods output PdiffSup=Sup;
```

run;

A robustness analysis of primary efficacy results will be assessed by repeating the primary analysis on the PP population.

Furthermore, the robustness of the results will be assessed by using another SAS procedure in the mITT, since the adjusted difference cannot be assessed directly from the proc logistic inducing a potential bias. Then the SAS procedure genmod will be used with identity link including treatment and country as covariates, using the following example of SAS code:

proc genmod data=ADCC(where=(PARAM='Successful overall preparation' and MITTFL='Y')); class TRTP(ref='KLEAN-PREP') COUNTRYC(ref='Largest country');

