class TRTP(ref='KLEAN-PREP') COUNTRYC(ref='Largest country'); model AVALC(EVENT='Yes') = TRTP COUNTRYC / link=identity; lsmeans TRTP / diff cl;

run;

No p-value will be displayed for the genmod model, since this would not be equivalent to the ones provided for the logistic procedure analysis.

In addition, the robustness of the results will be assessed in the mITT population by repeating the procedure logistic and estimating the 95 % CI of the treatment difference using the bootstrap method:

- The adjusted proportions will be estimated using the proc logistic model;
- 10'000 random samples will be generated using a proc surveyselect from the observed data with treatment and country as stratification and with seed=111;
- The adjusted proportions for each sample will be estimated using the same proc logistic model by replicate;
- The treatment differences will be derived for each sample;
- The 2.5 and 97.5 percentiles of the 10'000 estimated treatment differences will be considered for the 95 % CI of the treatment difference.

The following SAS code will be used:

```
proc logistic data=ADCC(where=(PARAM='Successful overall preparation' and
MITTFL='Y'));
    class TRTP(ref='KLEAN-PREP') COUNTRYC(ref='Largest country') /
    param=glm;
    model AVALC(EVENT='Yes') = TRTP COUNTRYC / link=logit firth;
    lsmeans TRTP / cl ilink;
    ods output lsmeans=lsm;
```

run;

proc transpose data=lsm out=_lsm;

var Mu; id TRTP;

run;

data diff;

```
set _lsm;
diff = EZICLEN - KLEAN-PREP;
```

run;

```
proc surveyselect data=ADCC(where=(PARAM='Successful overall preparation' and MITTFL='Y')) out=samples method=urs samprate=1 rep=10000 outhits seed=111; strata TRTP COUNTRYC;
```

run;

proc sort data=samples; by replicate; run;

proc logistic data=samples;

by replicate;

class replicate TRTP(ref='KLEAN-PREP') COUNTRYC(ref='Largest country') /
param=glm;
model AVALC(EVENT='Yes') = TRTP COUNTRYC / link=logit;
lsmeans TRTP / cl ilink;

ods output lsmeans=lsm_boot(keep=replicate TRTP Mu);

run;

```
proc sort data=lsm_boot; by replicate; run;
proc transpose data=lsm_boot out=_lsm_boot;
      var Mu;
      by replicate;
      id TRTP;
run;
data final;
      set _lsm_boot;
      diff = EZICLEN - KLEAN-PREP;
run;
proc sort data=final; by diff; run;
```

proc univariate data=final noprint;

var diff;

output out=ci95(rename=(Q2_5=Lower Q97_5=upper Q50=median)) pctlpre=Q pctlpts=2.5 50 97.5;

run;

No p-value will be displayed for this robustness analysis.

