3.2.12 Pooling of centres

It is not planned to perform subgroup analyses on individual or groups of centres but efficacy analyses will be adjusted on countries.

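### The primary analysis drops Firth from the main-effects model and turns equal-country LS means into pseudo-counts, so non-inferiority can be falsely declared when a small country is all successes

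*SAP*

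**What the plan says.** SAP 3.2.1.1 fits a logistic regression with treatment and country, and keeps their interaction only if p < 0.10. Firth's penalty is specified for the interaction model, "since there might otherwise be a quasi-complete separation of data points affecting the validity of the model". A note then states: "N.B.: TRTP*COUNTRYC, firth and ModelANOVA=TestInter will be removed if the interaction is not significant". The main-effects model, which decides the trial whenever the interaction is not significant, is therefore unpenalised.

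The adjusted proportion Mu for each arm comes from an LSMEANS statement with no observed-margins option, so every country counts equally on the logit scale whatever its size. Mu is converted to counts ("Count=Frequency*(1-Mu); output" for failures, and the matching line for successes). An unstratified PROC FREQ risk difference on those counts gives the interval compared with -15 points and the superiority test.

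The SAP acknowledges a difficulty, "since the adjusted difference cannot be assessed directly from the proc logistic inducing a potential bias", and adds an identity-link GENMOD analysis and a bootstrap as robustness analyses. On small countries, section 3.2.12 says only: "It is not planned to perform subgroup analyses on individual or groups of centres but efficacy analyses will be adjusted on countries".

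**The concern.** The SAP recognises the separation risk in one model and removes the protection in the other. A country in which every subject in both arms succeeds separates the main-effects model too. Its coefficient then has no finite maximum-likelihood value, and one K-th of whatever value the iteration reaches (K = number of countries) is added to the logit of both arms. Both Mu values rise towards 1, so their difference shrinks. The binomial standard error computed from Mu shrinks with it.

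The error favours declaring non-inferiority, and it affects the trial's one confirmatory decision. Apart from separation, Mu is not the success rate of the trial population: a country with 5 subjects per arm counts as much as one with 50. That can bias the result in either direction.

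**Working it through.** **Plan's own figure.** Inputs from Protocol 10.2: 85% success in both arms, margin 15 points, one-sided alpha 0.025, power 90%. n = (1.960 + 1.282)² x 2 x 0.85 x 0.15 / 0.15² = 119.1, so 120 per arm; 120/0.96 = 125. Both figures reproduce, and 120 per arm is used below.

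**Chance of the trigger.** At the margin (85% v 70%), a country with m subjects per arm is all successes with probability (0.85 x 0.70)^m: 21% for m = 3, 7.5% for m = 5, 0.6% for m = 10. Around 25 centres for 250 subjects (Protocol 3.1) is 10 per centre, so a country with one average centre has about 5 per arm.

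**Worked example** (constructed, five countries of 50/35/20/10/5 per arm):
- Eziclen 34, 24, 14, 7, 5 = 84/120
- Klean-Prep 42, 29, 17, 8, 5 = 101/120

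The crude difference is -14.2 points, 95% CI -24.6 to -3.7, so non-inferiority is not shown. The Firth interaction test is far from significant (p = 0.99), so the SAP moves to the unpenalised main-effects model.

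With the small country's coefficient stopped at 8 (v the largest country), the others are -0.016, 0.087 and -0.056, the intercept is 1.615 and the treatment effect is -0.834:
- Klean-Prep logit = 1.615 + (0 - 0.016 + 0.087 - 0.056 + 8)/5 = 3.218, so Mu = 96.15%.
- Eziclen logit = 3.218 - 0.834 = 2.384, so Mu = 91.56%.
- Difference = -4.6 points; SE = sqrt[(0.9156 x 0.0844 + 0.9615 x 0.0385)/120] = 3.09 points.
- Lower limit = -4.6 - 1.96 x 3.09 = -10.6, so non-inferiority is declared.

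| Method | Lower 95% limit (points) | Non-inferior? |
|---|---|---|
| Crude | -24.6 | No |
| SAP, coefficient stops at 5 | -15.3 | No |
| SAP, stops at 6 | -13.6 | Yes |
| SAP, stops at 8 | -10.6 | Yes |
| SAP, stops at 12 | -6.4 | Yes |
| Firth kept, rest as coded | -21.4 | No |
| Mantel-Haenszel | -24.6 | No |
| G-computation | -24.6 | No |

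The verdict depends on where the iteration stops.

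**Type I error.** The full two-stage SAP rule was coded in Python (SAS was not run), with true rates of 85% v 70% in every country, 20,000 trials per layout and Monte Carlo SE at most about 0.3 points.

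| Subjects per arm by country | As coded |
|---|---|
| 40/40/40 | 2.8% |
| 5 x 24 | 2.7% |
| 60/40/20 | 3.2% |
| 50/40/20/10 | 3.8% |
| 60/40/14/6 | 8.0% |
| 50/35/20/10/5 | 10.8% |
| 45/35/20/10/6/4 | 18.0% (8 iterations), 19.5% (25) |
| 50/40/27/3 | 22.7% |

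Across these layouts, keeping Firth gives 2.6-3.7%, and Mantel-Haenszel or g-computation gives 2.5-2.8%. In the four layouts with 6 or fewer per arm, non-inferiority was declared in roughly 86-100% of trials where a country separated, depending on layout and starting values.

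**Weighting fault without separation as the driver.** These runs use 50/35/20/10/5 with a true difference of -15 points in every country.
- Small countries better (control 82/84/88/92/95%): 30.1% as coded, 5.3% with Firth, 2.5% Mantel-Haenszel.
- Small countries worse (90/87/80/72/65%): 2.3%, 1.9% and 2.6%. With equal arms in this setting, power is 81% as coded v 91% Mantel-Haenszel.

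**Robustness analyses in the worked example.**
- *GENMOD.* The code names no distribution. A constrained binomial fit gives -13.0 (-23.2 to -2.8), with a fitted probability of 1.00 in the small country; a normal-error fit gives -14.2 (-24.7 to -3.6). Both fail the margin. However, "No p-value will be displayed for the genmod model", and no rule lets the analysis override the primary result.
- *Bootstrap.* The text says "The adjusted proportions for each sample will be estimated using the same proc logistic model by replicate", but the fit to the observed data carries firth and the replicate code, "model AVALC(EVENT='Yes') = TRTP COUNTRYC / link=logit", does not. Resampling is stratified by treatment and country, so a 10/10 country stays 10/10 in every replicate. The Firth point estimate is -11.7, yet the replicate interval is -7.8 to -1.1 (8 iterations) or -0.3 to 0.0 (25). With Firth in the replicates it is -20.5 to -3.4.

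**The case against.** The strongest objection is that the hazard needs a small country, and the documents give no country sizes. Less uneven layouts are harmless or nearly so: 30/25/25/20/20 gives 2.3%, 45/30/25/20 gives 3.1%, 50/30/20/12/8 gives 5.5%. SAP version 4.0 is dated 25 August 2020, after the planned end of the study in Q2 2020, so its authors probably knew the sizes. This stands as a limit on the practical risk. It does not make the written rule safe, because nothing in the SAP pools small countries or says what happens when one is all successes.

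The version 4.0 change log says a Firth option (printed as first) was added to the bootstrap for consistency with the primary model. This suggests that the authors think of the primary model as penalised and that the bootstrap mismatch is an incomplete edit. It does not cancel the note that removes the option.

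Detection is also planned: observed proportions with Wald intervals, the GENMOD fit, Firth results by country, review of log warnings, and raw LOGISTIC output in the report. A conflict would probably be noticed, but none of these outputs governs the decision.

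Finally, keeping Firth alone removes most of the inflation. That is true when countries are homogeneous. It still leaves 5.3% when small countries do better, so the equal weighting is a fault in its own right.

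**Conclusion.** The primary analysis is wrong as written and must be corrected before it is used. With a smallest country of about 6 per arm or fewer, false non-inferiority is about 3 to 9 times the nominal 2.5% (8.0/2.5 = 3.2; 22.7/2.5 = 9.1). With no small country the effect is negligible. Both the missing Firth penalty and the equal-weighted pseudo-counts contribute, the first far more than the second.

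The removal of Firth, the equal weighting and the pseudo-count step are read directly from the SAP code. The error rates rest on assumed country numbers and sizes, common success rates across countries except where stated, and an assumed stopping point for a fit that has no finite solution.

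**What to change.** Replace the pseudo-count step in SAP 3.2.1.1 with a risk difference standardised to the observed country mix. Fit the logistic model with firth in both the main-effects and interaction versions. Predict every subject's success probability under each treatment, average over the mITT population, take the difference, and use a delta-method SE. Compare the lower two-sided 95% limit with -15 points, then with 0 for superiority. The interaction rule can stay: standardise from whichever model it selects. This keeps the logistic regression with country that Protocol 10.4.5 specifies.

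A country-stratified Mantel-Haenszel risk difference on the real counts performs equally well. It would replace the protocol's model, would need an entry in SAP section 5, and would leave the interaction rule without a role. One method should be named, not both.

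Use the same model (with firth) and the same standardised difference in the bootstrap replicates. At the very least, strike firth from the list of items the note removes; this cures most of the inflation but not the weighting.

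The cost is SAP wording and a few lines of code, with no new data. In the homogeneous 85% v 85% case at 50/35/20/10/5, power is 89.7% with g-computation or 90.2% with Mantel-Haenszel, against 91.9% as coded and 90% planned.

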#### 10.4.5 Efficacy Evaluation

As indicated in Section 7.1, the primary efficacy variable is the proportion of subjects with successful overall preparation evaluated with the scale (from 1 to 4) of the Cleansing Score as assessed by the colonoscopist.

A successful preparation will be defined as excellent (4) or good (3) preparation.

A failure preparation will be defined as:

- Fair (2) or poor (1) according to bowel cleansing
- Any subject who did not have a colonoscopy based on the investigator's assessment of the cleansing (insufficient faecal output, unclear faecal discharge, etc.) or due to preparation related AEs.
- Any subject for whom cleaning was not adequate for evaluation.
- Any subject for whom rescue treatment (saline enema) was needed.

The proportion of subjects with successful colon cleansing (graded as excellent or good) will be summarised along with the 95% confidence interval (CI) using the standard Wald asymptotic CI. The primary efficacy endpoint will be analysed using a logistics regression model including country as stratified variable, the interaction between country and treatment will be also investigated. The formal hypothesis test result (p-value) for treatment difference will be presented together with a two-sided 95% CI for the difference in success rates. The non-inferiority will be demonstrated if the lower limit of the 95% CI of that difference is higher than -15%.

If the non-inferiority is demonstrated, the superiority will be analysed based upon treatment difference. If the lower limit of the CI is greater than zero, Eziclen®/Izinova® is proven to be superior to the Klean-Prep®.

Secondary efficacy endpoints are presented in Section 7.2.

Results will be tabulated by treatment group and overall using descriptive summary statistics (mean SD, median, interquartiles and ranges) or frequency count with two-sided 95% CI when appropriate.

Time to clear effluent data will be analysed by using survival methods. The results will be presented both in summary tables (number of events, censors, median and interquartile time to event with 95% CI...) and graphically in Kaplan-Meier plots by treatment group and overall. This will be detailed in the SAP.

Other secondary endpoints will be analysed using Cochran-Mantel-Hænszel (CMH) chi-square for count (percentage) adjusting for country effect and two-way analysis of variance (ANOVA) for continuous parameters including treatment, country and their interaction as covariates.

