1.4.4 Planned sample size

The primary aim of the study is to show that Eziclen®/Izinova® is non-inferior to Klean-Prep® in the proportion of subjects with successful colon cleansing.

A non-inferiority margin of 15 % has been selected for consistency with other studies in colon cleansing preparations.

Therefore assuming a success rate (excellent or good response) of 85 % in both the Eziclen®/Izinova® and Klean-Prep® groups, a one-sided alpha of 0.025 and 90 % power, 120 subjects are required per treatment group. Assuming a rate dropout/non-compliance to protocol of 4 % based on previous studies and taking into account that subjects will be hospitalised for treatment administration, 125 subjects will be randomised in each treatment

22/62

group, i.e. 250 subjects in total. Enrolment will be completed once 250 subjects have been randomised.

The primary endpoint of treatment success will be tested sequentially (hierarchical structure) with the first test being non-inferiority test based upon the treatment difference. A rejection of the null hypothesis will trigger superiority testing based upon the treatment difference.

The two hypothesis tests are hierarchically structured so that the second test (superiority) will only be considered if the first test (non-inferiority) is rejected. The superiority test is powered to detect an absolute difference of 18 %. There is no alpha adjustment for the second test as a result of the hierarchical testing.

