3.1.5 Significance testing and estimation

The primary endpoint of treatment success will be tested sequentially with the first test being a non-inferiority test based upon the treatment difference.

A two-sided 95 % confidence interval (CI) for the difference of the two clinical success rates (Eziclen®/Izinova® minus Klean-Prep®) will be calculated. If and only if the lower limit of the CI is greater than the lower limit of equivalence region -15%, Eziclen®/Izinova® will be proven to be not less effective than Klean-Prep®.

A rejection of the null hypothesis will trigger superiority testing based upon treatment difference. If the lower limit of the CI is greater than zero, Eziclen®/Izinova® will be proven to be superior to Klean-Prep®.

The secondary endpoints will be tested for descriptive purpose only.

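### The primary decision needs a two-sided 95% limit, but the SAP's only code for the primary difference saves the non-inferiority and superiority test tables at alpha=0.05 and never states the level of their limits

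*SAP*

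**What the plan says.** **The rule.** The design in SAP 1.4.4 assumes "a one-sided alpha of 0.025 and 90 % power, 120 subjects are required per treatment group". SAP 3.1.5 bases the decision on this: "A two-sided 95 % confidence interval (CI) for the difference of the two clinical success rates". It makes a lower limit above -15% both necessary and sufficient for non-inferiority, and a lower limit above zero the condition for superiority. SAP 3.2.1.1 repeats the first part: "The non-inferiority will be demonstrated if the lower limit of the 95 % CI of that difference is higher than -15" percent. Protocol 10.4.5 says the same: "The non-inferiority will be demonstrated if the lower limit of the 95% CI of that difference is higher than -15" percent.

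**The code.** SAP 3.2.1.1 explains that the logistic procedure gives no adjusted difference. It therefore turns the adjusted proportions into pseudo-counts and passes them to a frequency procedure. The first call is introduced by "The treatment difference and its p-value assessed for -15 % margin will be estimated using the" code that follows, and reads "table TRTP*AVALC / alpha=0.05 riskdiff(noninf margin=0.15 column=2); weight Count; ods output PdiffNoninf=NonInf". The superiority call reads "table TRTP*AVALC / alpha=0.05 riskdiff(sup column=2", closes the bracket and saves only its own table, `PdiffSup`.

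**Other uses of the code.** Later in 3.2.1.1, the by-country treatment differences and their 95% intervals are to come from this same frequency-procedure code. The bootstrap is a robustness analysis and is explicit about its level: "The 2.5 and 97.5 percentiles of the 10'000 estimated treatment differences will be considered for the 95 % CI". The identity-link model is also a robustness analysis.

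**The concern.** The text asks for one quantity and the code saves another. Each call runs a one-directional test, against the margin or against zero, with alpha=0.05 on the table statement. The one-directional design level is 0.025. Only the test tables are kept. No line of the primary-analysis code saves a two-sided 95% interval for the difference, yet that interval decides both confirmatory claims.

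If the limits in those tables use alpha one-sidedly, they are 100(1 - 2 x 0.05)% = 90% limits. A programmer who carries them into the table labelled 95% CI would be applying a one-sided 5% test without intending to. The by-country intervals would carry the same wrong label. The bootstrap interval, which is meant to check the primary result, would be compared with it at a different level.

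**Working it through.** **1. Which level the design rests on.** Inputs from SAP 1.4.4: 85% in both arms, margin 15 points, 90% power.

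n per arm = (z_alpha + z_beta)² x 2p(1 - p) / margin², with 2 x 0.85 x 0.15 / 0.15² = 11.33.

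- One-sided 0.025: (1.960 + 1.282)² x 11.33 = 119.1, so 120. This reproduces the SAP; 120 / 0.96 = 125 reproduces the number randomised.
- One-sided 0.05: (1.645 + 1.282)² x 11.33 = 97.1, so 98.

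The stated sample size therefore belongs to a two-sided 95% limit.

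**2. Half-width of the interval.** At 85% in both arms with 120 each, SE = √(2 x 0.85 x 0.15 / 120) = 0.0461. The half-width is 1.960 x SE = 9.03 points for 95% limits and 1.645 x SE = 7.58 points for 90% limits.

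**3. Error and pass rates.** Full enumeration of two binomials, 120 per arm, simple counts, Wald limits with unpooled SE:

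| True rates, Eziclen / Klean-Prep | Claim | 95% limits | 90% limits |
|---|---|---|---|
| 70 / 85 (on the margin) | non-inferiority, false | 2.6% | 5.2% |
| 65 / 80 (on the margin) | non-inferiority, false | 2.5% | 5.0% |
| 75 / 90 (on the margin) | non-inferiority, false | 2.8% | 5.4% |
| 85 / 85 | superiority, false | 2.6% | 5.2% |
| 85 / 85 | non-inferiority, true | 90.4% | 94.7% |
| 80 / 85 | non-inferiority, true | 54.1% | 66.2% |

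The non-inferiority verdict would differ in 94.7 - 90.4 = 4.3% of trials at 85/85, and in 66.2 - 54.1 = 12.1% at 80/85.

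**4. The SAP's own pseudo-count route.** The documents give no country split, so these are assumptions: three countries, equal true rates, adjusted proportions weighting countries equally, no interaction term, 100,000 simulated trials per run. For non-inferiority on the margin (70/85):

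- 40/40/40 per arm: error about 2.6 to 2.7% with 95% limits and 5.3% with 90% limits.
- 80/20/20 per arm: about 2.9 to 3.0% and 5.6 to 5.8%.

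Superiority at 85/85 stays near 2.5 to 2.6% and 5.0 to 5.3%. The error doubles, or nearly so, on this route too.

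**5. Results where the level decides.**

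- Simple counts, 95/120 against 102/120: difference -5.8 points, SE 4.94. The 95% limit is -5.83 - 1.960 x 4.94 = -15.5 (fails); the 90% limit is -5.83 - 1.645 x 4.94 = -14.0 (passes).
- The same totals through the pseudo-counts, 80/20/20 per arm, successes 63/16/16 against 68/17/17: difference -5.8 points, SE 4.91, 95% limit -15.4 (fails), 90% limit -13.9 (passes). The one-sided p-value against the margin is 0.030.
- Superiority, simple counts, 111/120 against 102/120: difference 7.5 points, 95% limit -0.4 (fails), 90% limit +0.8 (passes).

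**6. By-country intervals.** A 90% interval has 1.645 / 1.960 = 84% of the 95% width, so it is 16% too narrow. With an assumed 20 per arm and 85% in both arms, SE = 0.1129 and the half-width is 18.6 points instead of 22.1.

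**7. The other convention.** If alpha=0.05 is applied two-sidedly in the saved tables, their limits are 95% limits and every difference between the two levels above is zero.

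**The case against.** The strongest reply is that the rule is unambiguous and the 90% level is not in the documents. That is right. A reader might infer from the code that the trial will be run at a 5% one-sided error. The documents do not support this: the confidence level of the saved limits is software behaviour that they do not describe, and harm needs a second step, reporting those limits as the 95% interval against the SAP's own text.

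A reader might also infer that a one-sided p-value below 0.05 could be read as success. SAP 3.1.5 rules that out for non-inferiority, because the confidence limit there is a necessary as well as a sufficient condition. The p-values themselves do not depend on the alpha option. Stating their threshold in 3.2.1.1 is therefore only a clarification.

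The sentences introducing the two calls mention the difference and the p-values, not the decision limit. This weakens the point but does not remove it. The by-country text takes 95% intervals from the same code, and no other primary-analysis statement supplies one.

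SAP 4.3 requires double-programming of the primary endpoint, and SAP Appendix 2 includes the raw output. Either could catch a wrong level, provided someone compares it with the text. Two programmers who both used the saved tables would agree with each other. The table templates are in a separate document, so whether they name the source of the limit cannot be checked here.

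**Conclusion.** A mismatch between text and code stands and should be fixed: the SAP decides on a two-sided 95% limit, and its primary-difference code neither saves that limit nor states the level of what it does save. The consequence is conditional. If alpha is applied one-sidedly in the saved tables, and those limits are reported as the 95% interval, the error rises from about 2.6% to 5.2% for both claims at 120 per arm, and the by-country intervals are 16% too narrow. Otherwise there is no numerical effect. The figures assume Wald limits with an unpooled standard error. The SAP names Wald only for the single proportions, so this needs stating for the difference as well. The design, the margin, the sample size and the decision rule are consistent with one another and are not in question.

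**What to change.** In SAP 3.2.1.1:

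1. State that the decision limit is the lower limit of the two-sided 95% Wald interval for the adjusted difference: the estimate minus 1.960 times the unpooled standard error from the pseudo-counts.
2. Keep alpha=0.05 and save the table of two-sided risk-difference limits. Use it for non-inferiority, superiority, the per-protocol repeat and the by-country intervals, in place of the limits in `PdiffNoninf` and `PdiffSup`.
3. Add that the one-sided p-values are read at 0.025.
4. Before unblinding, run the code on dummy data and compute (estimate - reported lower limit) / SE from the same pseudo-counts. It must be 1.960. A value of 1.645 means 90% limits, and 2.241 means 97.5% limits.

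Setting alpha=0.025 on the table statement is not a safe shortcut. The option sits at table level and could turn the two-sided limits of the same call into 97.5% limits.

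The cost is two or three sentences, one added output table and one dummy-data run. No endpoint, margin or sample size changes.

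### The superiority p-value is coded without a margin, so, if PROC FREQ then applies a default of 0.20, it does not test the zero difference on which the SAP's superiority rule rests

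*SAP*

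**What the plan says.** The primary endpoint is tested in two steps, non-inferiority and then superiority, with no alpha adjustment for the second (SAP 1.4.4, 3.1.4 and 3.2.1.1; protocol 10.2).

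The superiority rule rests on the confidence interval for Eziclen/Izinova minus Klean-Prep. SAP 3.1.5 states: "If the lower limit of the CI is greater than zero, Eziclen®/Izinova® will be proven to be superior to Klean-Prep". SAP 3.2.1.1 and protocol 10.3 and 10.4.5 give the same rule. No section sets a superiority margin other than zero.

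SAP 3.2.1.1 then adds: "The following SAS code will be used to get the superiority p-value". The prescribed line is "table TRTP*AVALC / alpha=0.05 riskdiff(sup column=2", and the result is saved from the PdiffSup table. The non-inferiority call just above it does name its margin: "table TRTP*AVALC / alpha=0.05 riskdiff(noninf margin=0.15 column=2".

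SAP 1.4.4 and 3.2.1.1 also say that the superiority test is powered for an absolute difference of 18 points. Neither document says what margin the software uses when none is given.

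**The concern.** Both requests compare the difference with a margin. In the non-inferiority call the margin is written out and equals the planned 15 points. In the superiority call it is left to the software. If the software does not fill in zero, the printed p-value belongs to a different null hypothesis from the one in the SAP's text.

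SAP 3.2.1.1 asks for the formal p-value to be presented together with the two-sided 95% interval. A report could therefore show an interval wholly above zero beside a clearly non-significant superiority p-value, with nothing in the plan to say which is right.

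**Working it through.** **Inputs.** From SAP 1.4.4: "A non-inferiority margin of 15 % has been selected"; 85% success assumed in both arms; "a one-sided alpha of 0.025 and 90 % power, 120 subjects are required per treatment group"; superiority powered for 18 points. From SAP 3.1.5: superiority null of zero. Assumed, because the documents do not give it: the margin m used when none is stated. I take 0.20 as the PROC FREQ default and show 0 to 0.20. SAS was not available to run.

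**The plan's own sample size.** n = (1.960 + 1.282)² × 2 × 0.85 × 0.15 / 0.15² = 10.51 × 0.255 / 0.0225 = 119.1, so 120 per arm. Then 120 / 0.96 = 125. Both figures reproduce.

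**Which null fits the 18-point statement?** The SAP does not give the pair of rates. Taking 85% v 67% as an example:

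- SE = √[(0.85 × 0.15 + 0.67 × 0.33) / 120] = √(0.3486 / 120) = 0.0539.
- Power against 0: Φ(0.18/0.0539 − 1.960) = Φ(1.380) = 92%. With a pooled variance it is 90.9%, and 117 per arm suffice for 90%.
- Power against 0.20: Φ((0.18 − 0.20)/0.0539 − 1.960) = Φ(−2.331) = 1.0%.

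Against 0.20, a true 18-point gain lies inside the null hypothesis. For control rates of 67% to 80%, power is then 0.7% to 1.0%. The power statement is compatible with a null of zero and not with 0.20.

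**The p-value as a function of the margin.** Z = (d − m)/SE, one-sided, unpooled Wald variance, 120 per arm. The rates stand for the model-adjusted proportions that the SAP feeds into PROC FREQ.

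| Eziclen v Klean-Prep | d | SE | Lower 95% limit | m = 0 | 0.05 | 0.10 | 0.15 | 0.20 |
|---|---|---|---|---|---|---|---|---|
| 85% v 67% | 0.18 | 0.0539 | +7.4 points | 0.0004 | 0.008 | 0.069 | 0.289 | 0.645 |
| 95% v 85% | 0.10 | 0.0382 | +2.5 points | 0.004 | 0.095 | 0.500 | 0.905 | 0.996 |
| 90% v 60% | 0.30 | 0.0524 | +19.7 points | <0.0001 | <0.0001 | 0.0001 | 0.002 | 0.028 |

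For 95% v 85% in full: SE = √[(0.0475 + 0.1275) / 120] = 0.0382. At m = 0, Z = 0.10/0.0382 = 2.62 and p = 0.004. At m = 0.20, Z = −0.10/0.0382 = −2.62 and p = 0.996. The lower limit is 0.10 − 1.960 × 0.0382 = +0.025.

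All three rows are superior by the interval rule. At m = 0 every p-value is below 0.025 and agrees with it. At m = 0.20 none is.

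**Reach of the 0.20 case.** If the observed Klean-Prep rate is 80% or more, d cannot exceed 0.20, so p cannot fall below 0.5. At 75% (90 of 120), even 120 of 120 successes on Eziclen give Z = (0.25 − 0.20)/√(0.75 × 0.25/120) = 1.26, which is short of 1.96. At 70% (84 of 120), 119 successes would be needed, against 97 for a null of zero.

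**The case against.** The strongest objection is that the 0.20 default is not in the documents and was not run. That stands. What the documents alone establish is that the code leaves the null value unstated while the text fixes it at zero. The size of the error depends on the software and needs a test run.

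The second objection is that nothing is decided on this p-value. That also stands. Every statement of the rule refers to the lower confidence limit, which does not depend on the margin. A reader might infer that the trial could lose a superiority claim, or that non-inferiority is compromised. The documents support neither: superiority follows from the interval, the primary objective is non-inferiority alone, and that call has its margin written out. A positive margin is also conservative, so it cannot create a false superiority claim. At the planning assumption of equal rates, the interval rule would declare superiority only about 2.5% of the time.

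Third, a reader might infer that the p-value would always be near 1. It would not. At m = 0.20 it is 0.645 for 85% v 67% and 0.028 for 90% v 60%. The floor of 0.5 applies only when the observed control rate is 80% or higher.

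Finally, SAP 4.3 requires double programming for the primary endpoint, review for nonsensical results and cross-checking of outputs. These checks might catch the mismatch. They are not a full safeguard, because a second programmer following the same prescribed line would reproduce the same number.

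**Conclusion.** The point holds as a correction to prescribed code. The call for the superiority p-value states no margin, while the SAP's rule and its 18-point power statement both require a null of zero. If the omitted margin is taken as 0.20, the reported p-value answers a different question and can be non-significant when the interval shows superiority. If the default is 0, the number is right and only the explicit statement is missing. Intermediate margins give intermediate results, and any positive margin tests a different hypothesis from the rule.

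The figures assume 120 per arm and an unpooled Wald variance. The effect is confined to one reported p-value in the second hierarchical step, so this should be fixed but does not threaten the trial's conclusions.

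**What to change.** In SAP 3.2.1.1:

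- Replace the superiority call with a test of zero difference, for example `riskdiff(equal column=2)`, with the same Wald variance as the confidence interval.
- Save the matching ODS table instead of PdiffSup.
- State that the p-value is judged one-sided at 0.025 and must agree with the rule that the lower 95% limit exceeds zero.
- Before finalising, run the existing and the replacement lines once on dummy data such as 114 of 120 v 102 of 120 (95% v 85%). The correct one-sided p is 0.004; a value of 0.996 from the existing line would confirm the 0.20 default.

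The cost is a few lines of SAP code and text and one test run. Data, design and sample size do not change. The SAP's version history shows that code at this level is already under change control: version 3.0 clarified the primary-analysis code and version 4.0 added a single model option.
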